#### 4.2.2. Main analytical approach for primary endpoint

Participants achieving the primary efficacy endpoint of clinical symptom improvement with resolution at 24 hours  $\pm 4$  hours (refer definition in Section [4.2.1.](#)) will be estimated by frequency and percentage using CE24 set.

Exact Binomial (Clopper Pearson) 95% confidence limits for percentage of participants with clinical symptom improvement at 24 hours  $\pm 4$  hours will be computed. Participants who are not able to complete the CSS assessment at 24 hours ( $\pm 4$  hours) will be considered as 'treatment failure' and included as 'not improvers' in primary analysis.

A stacked bar graph will be produced for:

- Individual component of clinical symptoms by severity. (none/mild/moderate/severe) at 24 hours and baseline which will be presented using the ITT and CE24 sets respectively.
- Total clinical symptom score categories classified as (<2, 2-5, 6-8, 9-12) will be presented by visits using the ITT and CE24 sets.

- Percentage of participants with clinical improvement, clinical resolution, Clinical worsening and UTD by visits for CE24 set.

A descriptive summary will be presented for CSS total and individual scores (Dysuria, Frequency, Urgency, and Lower abdominal or Suprapubic pain) including n, mean, standard deviation (std), median, minimum, and maximum at each timepoint (24 hours  $\pm$  4 hours, 48 hours  $\pm$  4 hours, 72 hours  $\pm$  4 hours and 96 hours  $\pm$  4 hours) for the ITT set. Participants listings for clinical outcome and response will also be produced for ITT set.

#### 4.2.3. Sensitivity analyses for primary endpoint analysis

Sensitivity analysis will be conducted to examine the robustness of the primary efficacy results for the primary estimand. The sensitivity analysis will be performed using the CE24 set. A sensitivity analysis for the primary endpoint will be carried out to assess the impact for those participants who are unable to complete the CSS assessment at 24 hours ( $\pm$ 4 hours). Missing clinical improvement data (without any antibiotic use) will be imputed under the missing at random (MAR) assumption. If an antibiotic is taken for uUTI before or at the timepoint of CSS assessment and/or for other infections before the timepoint of CSS assessment, the outcome variable will be imputed as (“Participants without Clinical Improvement or Resolution”). Multiple imputation method will be implemented to impute the incomplete (missing) CSS at 24 hours ( $\pm$ 4 hours) using following steps -

Step 1: The missing clinical improvement with resolution outcome (without any antibiotics use) will be imputed using a logistic regression model. The following baseline covariates will be included in the imputation model. The number of imputations will be 1000 and SEED=219575.

- CCI
- 
- 
- 

Any participants who have a missing value for one or more model covariates listed above will be excluded from the imputation model. The participants with missing covariates will be classified as “Participants without Clinical Improvement or Resolution.”

Model for multiple imputation will be diagnosed to ensure the good fit for the data of clinical response.

Step 2: Step 1 will generate 1000 imputed datasets. From the imputed dataset, participants with clinical improvement will then be derived using the imputed and non-missing data per Section 4.2.1. and [Table 1](#)

Step 3: The estimated quantities in Step 2 will be combined across the imputed datasets using Rubin’s rules to provide pooled estimates for the clinical symptom improvement rate.

Percentage of participants with “Clinical improvement with resolution outcome” at 24 hours  $\pm$  4 hours will be estimated and its corresponding 95% (Wald) CIs will also be presented.

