Objectives, endpoints, and estimands: The primary objective of this study is to evaluate the clinical symptom improvement with gepotidacin treatment in female participants with uUTI at (24 hours [± 4 hours]). This will be evaluated by the number of participants who achieve clinical symptom improvement (without the need for other systemic antimicrobials), defined as a decrease from Baseline in CSS total score of at least 1 point at (24 hours [± 4 hours]). For additional information on the primary, secondary, and exploratory objectives and endpoints, refer to Section 3.

[figure not shown]
Overall design: This is a Phase 3b, open-label, single-arm, multicenter study to evaluate clinical symptom improvement and the safety of gepotidacin in female participants ≥ 12 years of age with clinical symptoms and urine dipstick findings suggestive of uUTI. Participants who meet eligibility requirements will receive gepotidacin 1500 mg administered orally as 2×750 mg tablets BID for 5 days. (Note: Each dose is to be taken after food consumption and with water to assist with tolerability.) Clinical symptom and safety assessments will be conducted throughout the study. The total duration of study participation is approximately 28 days, with at least 1 planned on site study visit and 6 telephone call study contacts (see Section 1.3 and Section 8 for study visit details), with allowance for unscheduled visits. For additional information on the overall design, refer to Section 4.1.

Number of participants: Approximately 90 participants will be enrolled in the study to ensure at least 82 evaluable participants are included in the primary analysis, such that the half width of the 95% CI is approximately $\leq 10\%$, under an assumption that 74% of participants meet the primary endpoint criteria as observed in the Phase 3 studies.

Data monitoring/other committee: This will be overseen by the GSK SRT (Section 10.9.6).

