#### **4.3.1.3. Sensitivity analyses for secondary endpoints**

Sensitivity analysis will be executed to investigate the robustness of the secondary efficacy outcomes (Outcomes are “Clinical Improvement with resolution” and “Clinical Resolution”).

This sensitivity analyses will measure the impact for those participants who are unable to complete the CSS assessment at each timepoint. Multiple imputation method will be used to impute the clinical outcome of interest at each timepoint (48 hours  $\pm 4$  hours, 72 hours

$\pm 4$  hours and 96 hours  $\pm 4$  hours) as described in Section 4.2.3. Step 1 & Step 2 with an additional covariate:

- **CCI**

Counts and percentage of participants with the outcome of interest at each timepoint and its corresponding 95% Exact Binomial CIs will be presented.

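### SAP 4.2.3 classes anyone with a missing imputation covariate as a failure: this conflicts with its own Step 2 for observed outcomes, and removes the MAR contrast where the 24 h outcome is missing too

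*SAP*

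**What the plan says.** - **Main analysis (SAP 4.2.2).** In the CE24 set, a participant without a 24 h CSS is a treatment failure.
- **Sensitivity analysis (Protocol 9.3.2.2).** Participants without a 24 h CSS are to be imputed by multiple imputation. Details are left to the SAP.
- **Imputation model (SAP 4.2.3, Step 1).** The missing improvement outcome is imputed under MAR by logistic regression, 1000 times. "The following baseline covariates will be included in the imputation model"; the list itself is redacted. Participants who took other systemic antimicrobials within the stated limits are set to failure.
- **Missing covariates (SAP 4.2.3, Step 1).** "Any participants who have a missing value for one or more model covariates listed above will be excluded from the imputation model". The next sentence begins "The participants with missing covariates will be classified as" and ends with the label for no improvement or resolution.
- **Derivation (SAP 4.2.3, Step 2).** Response is derived from the imputed values together with the non-missing ones, using 4.2.1 and Table 1.
- **Missing baseline CSS (SAP 4.2.1 and Table 1).** The outcome cannot be determined, which already counts as not improved.
- **Reuse.** SAP 4.2.4.1 and 4.3.1.5 refer back to 4.2.3. SAP 4.3.1.3 does so "as described in Section 4.2.3. Step 1 & Step 2 with an additional covariate", which is redacted.

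**The concern.** The sensitivity analysis exists to show how far the result depends on counting missing as failure. The covariate rule interferes with that in two ways.

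First, its wording covers all participants with a missing covariate, whether or not the 24 h outcome was observed. A logistic imputation model is fitted to participants with observed outcomes, so the group excluded from the model naturally includes some of them, and the next sentence classifies that group as failures. Step 2 implies that observed outcomes stand. A programmer cannot satisfy both sentences for a participant who improved but lacks a covariate.

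Second, even if the rule is meant only for participants with a missing outcome, those who also lack a covariate keep the main-analysis value. They receive no MAR imputation, although the section announces it for them.

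**Working it through.** **Inputs.** From the Protocol synopsis: "Approximately 90 participants will be enrolled in the study" "to ensure at least 82 evaluable participants are included in the primary analysis", with an assumed rate under which "74% of participants meet the primary endpoint criteria as observed in the Phase 3 studies". The precision target is worded "such that the half width of the 95% CI is approximately" 10% or less. The documents give neither the number of missing 24 h outcomes nor the number of missing covariates, so both are varied here as assumptions.

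**The plan's own figure.** At 74%, the Clopper-Pearson 95% interval for n = 82 runs from 63.1% to 83.1%, a half-width of (83.1 − 63.1)/2 ≈ 10.0% (9.97% unrounded). At n = 80 the half-width is 10.09%, and 82 is the smallest n that meets the target. The sample size reproduces and is not affected by this point.

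**Effect of one participant.** Recoding one observed improver costs 1/82 = 1.22 points. Averaged over participants who improve with probability 0.74, the cost is 0.74/82 = 0.90 points.

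**Notation.** Let k be the number with a missing 24 h outcome, m the number with a missing covariate, and j the number with both. Assume 74% true response in every subgroup. Expected estimates are:

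- main analysis, missing = failure: 0.74 × (82 − k)/82
- MAR with observed outcomes kept and all missing outcomes imputed: 74.0%, whatever k and m
- 4.2.3 read literally: 0.74 × (82 − m)/82
- 4.2.3 read narrowly (failure only if the outcome is missing too): 0.74 × (82 − j)/82

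The three expressions that vary share one form, so one table serves all of them:

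| Number set to failure (k, m or j) | Estimate |
|---|---|
| 0 | 74.0% |
| 1 | 73.1% |
| 2 | 72.2% |
| 4 | 70.4% |
| 8 | 66.8% |

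**Literal reading.** With k = 2 and m = 4, the main analysis gives 72.2% and the nominal MAR analysis 70.4%. That ordering is incoherent: with observed outcomes kept, missing = failure is the lowest value the data allow, so a MAR estimate cannot properly fall below it. This happens whenever m exceeds k.

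**Narrow reading.** With k = 2 and j = 0, the contrast is complete: 74.0% against 72.2%. With j = k, both analyses give the same number and the comparison carries no information. Values of j in between give a partial contrast.

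**When the rule has no effect.** If covariates are complete, m = j = 0 and both readings give 74.0%. If the missing covariate is baseline CSS, the outcome is already undetermined and counted as not improved, so the rule changes nothing.

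**The case against.** The best defence is context. The stated aim of 4.2.3 concerns participants who could not complete the 24 h CSS, Step 1 is about imputing the missing outcome, and the covariate rule sits inside Step 1. Step 2 then uses observed values. On that view observed outcomes are safe, and the sentence is merely loose. Baseline data are collected onsite before the first dose, so few covariates may be missing. The study is single-arm with no hypothesis test, and its main analysis is already the most pessimistic treatment of missing outcomes.

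Much of this stands. A reader might infer that the SAP intends to overwrite observed outcomes; it never says so, and Step 2 points the other way. What is established is a conflict between two sentences.

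A reader might also infer that the analysis fails to test the missing-data assumption at all. That is not supported, because MAR imputation does replace missing = failure for everyone with a missing outcome and complete covariates.

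Nor is a model with baseline covariates only an invalid MAR model. The 24 h call is the first planned post-baseline CSS, so no earlier post-baseline score was left out.

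Finally, a reader might suppose that the covariate added in 4.3.1.3 is post-baseline and so prone to be missing in the same participants. It is redacted, and nothing can be argued from it.

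The defence does not reach the narrow reading. Participants lacking both outcome and covariate are assigned failure on any interpretation.

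**Conclusion.** The point holds as a wording conflict plus a limited gap in the sensitivity analysis. SAP 4.2.3 does not confine the missing-covariate rule to missing outcomes and does not reconcile it with Step 2. For participants missing both items, it restores the rule it is supposed to relax.

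On the literal reading the size is 1.2 points per observed improver recoded. For one to five participants with a missing covariate and an observed outcome (an assumed range), the average loss is 0.9 to 4.5 points (0.90 × 1 to 0.90 × 5). On the narrow reading no observed outcome is lost, and the harm is a reduced contrast with the main analysis, in proportion to j. These figures assume N = 82 and 74% response in every subgroup. The actual effect may be zero. The primary estimate and the sample size are untouched. The change is worth making before the analysis is run because it is cheap and removes a choice that would otherwise fall to the programmer.

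**What to change.** In SAP 4.2.3:

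1. State that an observed 24 h outcome is always kept, whatever covariates are missing.
2. Delete the rule that classes participants with missing covariates as failures. Impute the missing covariates instead, for example by fully conditional specification.
3. Keep assignment to failure only for antimicrobial use as already defined, and for a missing baseline CSS, where the outcome is already undetermined.

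As an improvement rather than a correction, add the CSS at 48, 72 and 96 h to the imputation model as auxiliary variables. They are collected in any case, and would inform the imputed value for someone who missed only the 24 h call.

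Carry the same changes into 4.2.4.1, 4.3.1.3 and 4.3.1.5. The cost is a SAP amendment and a standard change of imputation method. No new data are needed.

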##### **4.2.4.1. Sensitivity analysis of supplementary estimand for primary endpoint**

- A sensitivity of the supplementary estimand for primary endpoint will be performed according to the rule mentioned in Section 4.2.4. considering ITT analysis set. The multiple imputation method will be used to impute the Responders (participants who achieve clinical symptom improvement) at 24 hours ( $\pm$ 4 hours) as described in Section 4.2.3. step 1 & step 2.

Percentage of participants clinical symptom improvement at 24 hours  $\pm$  4 hours will be estimated and its corresponding 95% Exact Binomial CIs will also be presented.

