#### **4.3.1.4. Supplementary estimand for secondary endpoint analyses**

A supplementary estimand analyses for secondary endpoints will be performed if **CCI** of participants in the ITT analysis set are unable to take  $\geq 80\%$  doses of gepotidacin up to each of 24 hours  $\pm 4$ , 48 hours ( $\pm 4$  hours), 72 hours ( $\pm 4$  hours), and 96 hours ( $\pm 4$  hours). The supplementary estimand analysis will be performed using ITT analysis set. Participants who are unable to complete the CSS assessment at each timepoint (24 hours  $\pm 4$ , 48 hours ( $\pm 4$  hours), 72 hours ( $\pm 4$  hours), and 96 hours ( $\pm 4$  hours)) will be considered treatment failures and included in the analysis as not improved or not resolved for clinical symptom resolution.

Counts and percentage of participants with clinical symptom improvement and resolution at each timepoint and its corresponding 95% Exact Binomial CIs will be presented.

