#### **4.3.1.5. Sensitivity analyses of supplementary estimand for secondary endpoints**

Sensitivity of supplementary estimands analyses for secondary endpoints will be performed according to rule mentioned in Section 4.3.1.4. considering ITT analysis set. Multiple imputation method will be used to impute the missing outcome at each timepoint (24 hours  $\pm 4$ , 48 hours  $\pm 4$  hours, 72 hours  $\pm 4$  hours and 96 hours  $\pm 4$  hours) as described in Section 4.2.3 for clinical symptom improvement and resolution, respectively.

[figure not shown]
Counts and percentage of participants with “Clinical improvement with resolution outcome” at each timepoint and its corresponding 95% (Wald) CIs will be presented.

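### Does the label improvement with resolution turn the SAP's sensitivity analyses into analyses of complete resolution?

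*SAP*

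**What the plan says.** The primary endpoint (SAP 1.1 and 4.2.1) is a fall in total CSS of at least 1 point at 24 hours without other systemic antimicrobials. SAP 4.2.1 counts a participant as improved if she attains either of two Table 1 labels, *improvement with resolution* or *improvement without resolution*, and says that resolution is included.

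SAP 4.2.3 names its target in two ways:

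- Step 1: "The missing clinical improvement with resolution outcome (without any antibiotics use) will be imputed using a logistic regression model".
- Step 2: "participants with clinical improvement will then be derived using the imputed and non-missing data", with a pointer to 4.2.1 and Table 1.
- Step 3 applies Rubin's rules "to provide pooled estimates for the clinical symptom improvement rate".
- Closing sentence: "Percentage of participants with “Clinical improvement with resolution outcome” at 24 hours".

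SAP 4.2.4.1 reuses Steps 1 and 2 and says that the method is "used to impute the Responders (participants who achieve clinical symptom improvement").

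For the secondary endpoints, 4.3.1.3 states "Outcomes are “Clinical Improvement with resolution” and “Clinical Resolution". SAP 4.3.1.4 reports "Counts and percentage of participants with clinical symptom improvement and resolution at each timepoint". Its sensitivity analysis in 4.3.1.5 imputes "for clinical symptom improvement and resolution, respectively", but its closing sentence names only the *improvement with resolution* outcome.

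Table 1 has two rows that a CSS of 0 satisfies: *Clinical Improvement with Clinical Resolution* and *Clinical Resolution*. The outcome bar chart in 4.2.2 lists improvement, resolution, worsening and unable to determine, but not *No Change*.

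**The concern.** In Table 1 the *with resolution* label means complete resolution only. A programmer who matched the closing sentence of 4.2.3 to that row would report the share with CSS 0. The sensitivity analysis exists to be set beside the main improvement rate, so that the difference shows the effect of missing CSS. If the two results were different endpoints, the comparison would say nothing about missing data. Under the same reading, 4.3.1.3 would analyse CSS 0 twice and improvement not at all.

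Table 1 raises a second worry. If the outcome variable held one label per participant, either choice for CSS 0 would break a rule. Coded as *Clinical Resolution*, she would fail for improvement, because 4.2.1 fails every label outside its two. Coded as *with resolution*, she would not be credited under 4.3.1, which names only *Clinical Resolution*.

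**Working it through.** **1. The plan's own figure.** Protocol 1.1 gives 82 evaluable participants, an assumed rate of 74% and a 95% CI half-width of about 10% or less. The Clopper-Pearson limits for x events in n are the 2.5% quantile of Beta(x, n−x+1) and the 97.5% quantile of Beta(x+1, n−x). With np left unrounded at p = 0.74, the half-width is 10.03% at n = 81 and 9.97% at n = 82, so 82 reproduces. The nearest whole count is 61/82 = 74.4%, with CI 63.6% to 83.4% and half-width 9.9%. This is the reference case below.

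**2. What 4.2.3 produces when followed step by step.**

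- Its introduction says that missing improvement data are to be imputed.
- It twice names the non-event class as participants with neither improvement nor resolution. The event is therefore improvement or resolution. An event of CSS 0 alone would not have that complement.
- Step 2 derives improvement under 4.2.1, and Step 3 pools the improvement rate.

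Let m be the number of the 82 with missing CSS, all counted as failures in the main analysis. The 61 observed improvers stay improved in every imputed dataset, because Step 2 uses the observed data under 4.2.1. Hence

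61/82 ≤ pooled rate ≤ (61 + m)/82.

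This holds even if Step 1 were programmed with a CSS-0 indicator, because that can alter only the m imputed values. The wording of Step 1 can therefore shift the result by at most m/82. The documents do not give m. For assumed values:

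| m | m/82 |
|---|---|
| 2 | 2.4 points |
| 4 | 4.9 points |
| 8 | 9.8 points |

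Under the intended reading the shift due to wording is nil.

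**3. The secondary sections.** Reading 4.3.1.3 literally makes its two named outcomes the same, which is a reason to reject that reading. SAP 4.3.1 says that improvement includes resolution, and 4.3.1.1 says with and without resolution.

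**4. Table 1.** CSS runs from 0 to 12 (four symptoms scored 0 to 3). SAP 4.1.2 removes baseline scores below 2 from the ITT and clinically evaluable sets. Baseline 2–12 against follow-up 0–12 gives 11 × 13 = 143 pairs. With the antimicrobial conditions met:

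| Table 1 rows met | Pairs |
|---|---|
| *With resolution* and *Clinical Resolution* | 11 |
| *Without resolution* only | 66 |
| *No Change* only | 11 |
| *Worsening* only | 55 |

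Only CSS 0 meets two rows, and it meets both every time. The endpoint rules fit that: 4.2.1 credits the first row for improvement and 4.3.1 credits the second for resolution. The list in 4.3.1 of outcomes that do not count as resolved leaves out the *with resolution* label. SAP 4.1.3 speaks of outcome variables in the plural, which suits two flags.

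**5. The bar chart.** In the reference case 82 − 61 = 21 (25.6%) are not improved. If improvement and resolution are drawn as exclusive segments, leaving out *No Change* makes the bar 0 to 25.6 points short of 100%. The chart is descriptive and no estimate uses it.

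**The case for a change.** The case for a change is that outcomes are determined by program, so Table 1 and the closing sentence of 4.2.3 act as a specification. If R participants reach CSS 0, a literal output is R/82. At an assumed R of 8, 16, 25 or 41 it reads 9.8%, 19.5%, 30.5% or 50.0% against 74.4%, far more than missing data could explain. Even a correctly programmed table would mislead if it carried the quoted label. Clearer wording was available, since 4.2.4.1 uses it.

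The size does not stand. R/82 arises only if Steps 2 and 3 are set aside, and it leaves out the imputed events, so it is not a multiple-imputation result for any m above 0. R is not in the documents, and the full range of the gap, 0 to 74.4 points, tells the reader nothing. SAP 4.2.2 uses the same phrase, and there the pointer to 4.2.1 settles the meaning. Step 2 of 4.2.3 has the same pointer.

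Three smaller points stand. The label is poor and should not become a table title. No sentence says outright that a CSS-0 participant carries both Table 1 labels. The closing sentence of 4.3.1.5 omits resolution, although the section imputes it and the analysis it supports reports it. That section also depends on a compliance trigger, whose threshold is blacked out, so the output may never be needed.

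**Conclusion.** No change to the plan follows. The wording is inconsistent, but an analyst who carries out 4.2.3 as written obtains the improvement rate including resolution. The effect on the primary rate, the estimand, the imputation model and the sample size is nil. If Step 1 alone were misread, the sensitivity result would move by at most m/82 (4.9 points at an assumed m of 4), and Step 2 would still hold the observed improvers in place. This rests on two things: Steps 2 and 3 and 4.2.1 are followed, and improvement and resolution are derived as separate flags from the scores, which the endpoint definitions support. The unnamed resolution output in 4.3.1.5 and the absent *No Change* segment are details that analysts fill sensibly when they lay out the tables and figures. Rewording would make the text easier to read but would alter no estimate or conclusion.
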